Date of protocol: 10/14/2020

IRB Approval Date: 11/24/2020

Version of protocol: 7

IND number: 139015

Institutional protocol number: OSU 17102

DLT definition	

• Acute GVHD <math>\geq</math> Grade 3

• Any non-hematologic toxicity <math>\geq</math> Grade 3 related to Daratumumab

• Hematologic toxicity: grade 4 toxicity not related to the underlying disease and not responding to growth factor or transfusion within 7 days

• Grade 3 or higher non-neurologic immune-related adverse events (e.g. diarrhea, pruritus, rash) that responds to corticosteroids and improve to grade 1 or less within 4 weeks will NOT count as DLTs. Optional biopsy of affected organs will be encouraged to help determine whether the immune-related condition is due to GVHD

Enrollment schedule	
Dose level 1: Weekly Dara for eight doses; if no infusional toxicity observed or GVHD observed, proceed to next dose level. 3 patients at a time can be enrolled in one dose level.
 
If no GVHD is observed after at least 2 weeks after DLI, enrollment will proceed to next dose level.

Definitions for safety-evaluability	Received at least one dose of Daratumumab
Definition for DLT evaluability	
All patients are evaluable for DLT except patients who are unable to receive 3 doses of daratumumab in dose level 1, or 3 doses of daratumumab and DLT for dose levels 2 and 3 due to progression of AML.
 
DLT observation period will be from the first dose of daratumumab till 7 days post 3rd dose of daratumumab (for dose level 1) and from the first dose of daratumumab till at least 4 weeks post DLI (for dose level 2 and 3)

Definitions for efficacy evaluability:	All eligible patients who receive at least one dose of Daratumumab, do not withdraw consent, and are evaluated for response at week 8.
Dose-limiting toxicity:	Grade 3 or 4 GVHD
Special situations	

1. If patients attain response before DLI, there will be three options at the discretion of treating physician :

a. Proceed with DLI

Date of protocol: 10/14/2020

IRB Approval Date: 11/24/2020

Version of protocol: 7

IND number: 139015

Institutional protocol number: OSU 17102

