	

b. Continue Daratumumab maintenance( If Daratumumab is given as maintenance, a schedule of 16mg/kg every 2 weeks for 16 (8 doses) weeks and then monthly for 6 months will be administered)

c. Proceed with second transplant.

 
2. If patients develop steroid-responsive GVHD and remission before DLI, there will be two options at the discretion of treating physician :
 

a. Continue Daratumumab maintenance (If Daratumumab is given as maintenance, a schedule of 16mg/kg every 2 weeks for 16 weeks (8 doses) and then monthly for 6 months will be administered)

b. Proceed with second transplant.

--	---

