## 9.6 DEFINITIONS OF DOSE LIMITING TOXICITY

Dose limiting toxicity would be development of Grade 3-4 GVHD. GVHD will be graded according to the Glucksberg criteria.

Dose-limiting toxicity is defined as:

- Grade 3-4 Acute GVHD
- Any Grade 3-4 non-hematologic toxicity related to Daratumumab
- Hematologic toxicity: grade 4 toxicity not related to the underlying disease and not responding to growth factor or transfusion within 7 days

Date of protocol: 10/14/2020

IRB Approval Date: 11/24/2020

Version of protocol: 7

IND number: 139015

Institutional protocol number: OSU 17102

Grade 3 or higher non-neurologic immune-related adverse events (e.g. diarrhea, pruritus, rash) that respond to corticosteroids and improve to grade 1 or less within 4 weeks will NOT count as DLTs. Optional biopsy of affected organs will be encouraged to help determine whether the immune-related condition is due to GVHD. Once a patient develops Grade 3-4 GVHD, further enrollment will be on hold until safety and monitoring committee assesses toxicity.

For patients developing Grade 2 GVHD, further doses of Daratumumab will be held until GVHD is controlled. Patients have to meet above-listed criteria before they can resume Daratumumab.

In the phase II expansion part of the study, if >2 patients develop  $\geq$  Grade 3 GVHD, we will stop enrollment and reassess safety.

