If a patient in dose level 1 receives less than 3 doses of Daratumumab due to reasons other than toxicity, then this patient will not be evaluable for DLT and will be replaced. An additional patient will be added to the dose cohort. For dose level 2 or 3, if a patient does not receive 3 doses of Daratumumab and DLI due to reasons other than toxicity, then this patient will not be evaluable and will be replaced. There will be no intrapatient dose escalation. Phase I may involve as few as 3 patients (three at the starting dose level if  $\geq 2$  DLTs are experienced) and a maximum of 18 patients will be treated, six at each of the 3 dose levels. We assume that 10% of the patients in this group will not be evaluable due to not finishing the DLT observation period. So we expect to accrue a minimum of 4 patients and a maximum of 20 patients.

At OSU, 125 patients with AML/MDS underwent allo-HSCT in 2012 and 2013. Among these, 32 patients relapsed. About 40% were from related donor and 60% from unrelated donor. So we expect to accrue approximately 6 patients for the related sibling donor cohort and 10 patients for the unrelated donor cohort per year. Hence, the minimum study duration for phase I would be about 8-10 months and the maximum study duration would be around 2.5-3.5 years (accounting for the DLT observation period) for related sibling donors and unrelated donors respectively.

After the MTD has been established, we will expand to Phase II trial. For phase II part, considering that patients receiving transplant from related sibling donor or unrelated donor with each treated at the corresponding MTD of Daratumumab plus DLI are expected to have similar profiles for response and toxicities, we will combine these 2 cohorts together in phase II stage. The null hypothesis is that combination of Daratumumab and DLI has a response rate of < 10% in patients with relapsed AML following allo-HSCT. The alternative hypothesis is that Daratumumab has a response rate of at least 30% in patients with relapsed AML following allo-HSCT. With a type 1 error (alpha): 0.05, and a type 2 error (beta = 1 – power): 0.20, the sample size would be 25 patients for Phase II. If the number of patients achieving ORR is 6 or more, then we reject the null hypothesis. We would include 3-6 patients from

Date of protocol: 10/14/2020

IRB Approval Date: 11/24/2020

Version of protocol: 7

IND number: 139015

Institutional protocol number: OSU 17102

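### At dose levels 2 and 3 the replacement rule, read plainly, keeps a patient who misses DLI because of a toxicity below DLT grade in the 3+3 denominator with no DLT, although that patient gives no information on the DLI dose

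*Combined protocol and SAP*

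**What the plan says.** Section 16 gives the replacement rule for the DLI levels. Its condition reads "For dose level 2 or 3, if a patient does not receive 3 doses of Daratumumab and DLI due to reasons other than toxicity"; anyone who meets that condition drops out of the DLT count, and another patient is enrolled instead. The rule does not separate a DLT from a lesser toxicity, and it does not state how a patient is counted who misses DLI for a lesser toxicity.

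The synopsis row on DLT evaluability starts from inclusion: "All patients are evaluable for DLT except patients who are unable to receive 3 doses of daratumumab in dose level 1". Its only exception at the higher levels is "3 doses of daratumumab and DLT for dose levels 2 and 3 due to progression of AML", where the second DLT appears to be a slip for DLI.

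Section 9.6 sets the GVHD threshold for a DLT at "Grade 3-4 Acute GVHD". Below it, "For patients developing Grade 2 GVHD, further doses of Daratumumab will be held until GVHD is controlled". Immune-related events of Grade 3 or higher, other than neurologic ones, that respond to steroids and "improve to grade 1 or less within 4 weeks will NOT count as DLTs".

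The synopsis row on special situations adds: "If patients develop steroid-responsive GVHD and remission before DLI, there will be two options at the discretion of treating physician". The two options are daratumumab maintenance and a second transplant; neither is DLI.

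The escalation table in Section 16 counts patients with a DLT. For levels 2 and 3 the observation period runs from the first daratumumab dose to no less than four weeks after DLI. No section sets a minimum number of DLI-exposed patients before a level is cleared or an MTD declared.

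**The concern.** Daratumumab is fixed at every level and the 3+3 is there to find the MTD of the DLI. Only patients who received the DLI inform that dose. The exception for toxicity has a good purpose: it stops a patient with a DLT from being discarded. But it is worded for all toxicity, so it also retains patients whose toxicity was not a DLT and who never received donor lymphocytes. Each such patient enters the table as a zero at a dose that he or she was not given.

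The plan leaves room for such patients in at least three ways:

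- Steroid-responsive GVHD with remission before DLI (synopsis, special situations).
- A daratumumab hold for Grade 2 GVHD that outlasts the DLI window. Section 9.3 ties the DLI to the 72 hours after a daratumumab dose and places it in weeks 3-4; Section 7.1 says weeks 3-5, and the two should be reconciled.
- Refusal of further treatment because of lesser toxicity, which Section 16.2 expects to record.

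At stake are the escalation decision, the declared MTD, and the dose carried into Phase II. Section 16 also brings 3-6 Phase I patients treated at the MTD into the Phase II analysis.

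**Working it through.** **1. The plan's own evaluability figure.** Section 16 assumes 10% unevaluable and expects 4 to 20 patients per cohort. 3 / 0.9 = 3.33, rounded up to 4; 18 / 0.9 = 20. Both reproduce and are not disputed.

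**2. How each rule classifies a level 2/3 patient who receives no DLI and has no DLT.**

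| Reason DLI was missed | Section 16 | Synopsis |
|---|---|---|
| AML progression | replaced | not evaluable |
| Response, or second transplant | replaced | evaluable |
| Toxicity below DLT grade | not replaced | evaluable |

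The second row is a conflict between the two places. In the third row they agree, and the patient stays in. That this patient then counts as a non-DLT is an inference: no DLT criterion is met, and no rule counts the patient otherwise.

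**3. Effect on escalating past level 2.** Input from Section 16: escalate after 0 DLTs in 3, or after 1 in 3 followed by 0 in a further 3. Assumptions, since the documents give no figures: a true DLT rate p among DLI recipients, no DLT risk in an unexposed patient, and a fully exposed second group of three. With n exposed patients among the first three,

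P(escalate) = (1-p)^n + n p (1-p)^(n-1) × (1-p)^3.

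At p = 0.40:

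- n = 3: 0.216 + 0.432 × 0.216 = 0.309
- n = 2: 0.360 + 0.480 × 0.216 = 0.464

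| Assumed p | All three exposed | One of three unexposed |
|---|---|---|
| 0.33 | 0.434 | 0.582 |
| 0.40 | 0.309 | 0.464 |
| 0.50 | 0.172 | 0.312 |

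**4. Averaged over an assumed frequency.** If each counted patient is unexposed with probability q, the effective rate is e = p(1-q), and P(escalate) = (1-e)^3 × [1 + 3e(1-e)^2]. At p = 0.40:

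- q = 10%: e = 0.36, and 0.2621 × (1 + 0.4424) = 0.378
- q = 20%: e = 0.32, and 0.3144 × (1 + 0.4439) = 0.454

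**5. The MTD criterion.** Level 3 is the top level, so step 3 does not describe it. The MTD definition, at most one DLT in six, can apply there. With m exposed patients among the six, the chance of meeting it is (1-p)^m + m p (1-p)^(m-1). At p = 0.40:

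- m = 6: 0.0467 + 0.1866 = 0.233
- m = 5: 0.0778 + 0.2592 = 0.337

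**The case against.** Four points can be made in defence of the plan.

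*Other text restrains escalation.* The synopsis enrollment row lets enrollment move up when no GVHD has been seen for at least two weeks after DLI, and Section 14.1 has the monitoring committee decide on further enrollment whenever GVHD is identified. A reader might infer from the replacement rule that escalation follows automatically in the GVHD examples. The documents do not support that: either provision may stop it. But neither changes who is in the denominator, neither appears in the Section 16 table, and neither reaches a refusal for a toxicity other than GVHD.

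*The window implies exclusion.* An unexposed patient cannot complete a window that ends after DLI, and Section 16 describes the 10% unevaluable as those who do not finish it. That sentence is a planning assumption for accrual. It does not override the explicit replacement rule, although it shows that the intention may have been different.

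*Section 9.6 does not stop treatment.* A reader might infer that Grade 2 GVHD, or a steroid-responsive immune event, ends treatment and so removes the DLI. This part of the objection stands. Grade 2 GVHD only pauses daratumumab, which may resume, and the immune events are said not to be DLTs, with nothing about stopping treatment or omitting DLI. The Grade 2 route therefore matters only if the hold outlasts the DLI window, and the immune-event clause alone does not show that a DLI would be missed.

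*The special situation is narrow.* It needs both GVHD and remission. If remission is recorded as the reason for no DLI, Section 16 replaces the patient; if the GVHD was Grade 3-4, it may already be a DLT. This is fair, but it leaves the classification to whichever reason is written down.

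**Conclusion.** The point holds as a defect in the evaluability rule. Section 16 and the synopsis both leave a patient who misses DLI for a toxicity below DLT grade in the denominator, and under the synopsis alone, patients who skip DLI for response or second transplant stay in as well.

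The size is conditional. One unexposed patient among the first three at level 2 adds about 0.14 to 0.16 to the chance of escalating over assumed DLT rates of 0.33 to 0.50. If 10% of counted patients are unexposed, the rise at 0.40 is about 0.07 (0.309 to 0.378). These figures assume no DLT risk without DLI. The window opens at the first daratumumab dose and daratumumab-related toxicity can be a DLT, so a background rate would narrow the gap.

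A reader might go further and conclude that the MTD will rest on untested doses. The documents do not show that: they give neither the frequency of missed DLI nor a DLT rate, and committee review may intervene. The Phase II decision rule of 6 or more responders in 25 is not affected. Nothing here bears on whether DLI should be given after such a toxicity.

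**What to change.** Reconcile Section 16 and the synopsis evaluability row to one rule, and correct the apparent slip of DLT for DLI in the synopsis. Suggested wording:

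*At dose levels 2 and 3 a patient counts for DLT assessment if (i) a DLT occurred, whether or not DLI was given, or (ii) three daratumumab doses and the assigned DLI were received and the observation window was completed without a DLT. All other patients are replaced, whatever the reason. Their toxicities are reported separately at the escalation review.*

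Part (i) keeps the protection that the present wording was meant to give, and the separate report keeps lesser toxicities in view. No dose or clinical rule changes. The cost is a wording amendment, an occasional replacement patient and a short delay in Phase I.

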## 7 STUDY DESIGN

### 7.1 OVERVIEW OF STUDY DESIGN

This is a phase I/II study that evaluates combination of Daratumumab and escalating doses of donor lymphocyte infusions. Donor lymphocyte infusions will be given within 72 hrs. of daratumumab dose. The following dose levels are used.

1. Phase I study with the following dose levels for related sibling donors:
  - a. Dose level 1: Dara 16mg/kg
  - b. Dose level 2: Dara 16mg/kg + DLI (1 infusion at any time between weeks 3-5) : 1x10e6 CD3/kg
  - c. Dose level 3: Dara 16mg/kg + DLI (1 infusion at any time between weeks 3-5): 1x10e7 CD3/kg
2. Phase I study with the following dose levels for unrelated donors:
  - c. Dose level 1: Dara 16mg/kg
  - d. Dose level 2: Dara 16mg/kg + DLI (1 infusion at any time between weeks 3-5): 1x10e5 CD3/kg
  - e. Dose level 3: Dara 16mg/kg + DLI (1 infusion at any time between weeks 3-5): 1x10e6 CD3/kg
3. Phase I study with the following dose levels for haploidentical donors:
  - f. Dose level 1: Dara 16mg/kg
  - g. Dose level 2: Dara 16mg/kg + DLI (1 infusion at any time between weeks 3-5): 1x10e4 CD3/kg
  - h. Dose level 3: Dara 16mg/kg + DLI (1 infusion at any time between weeks 3-5): 1x10e5 CD3/kg

Patients with MRD will not be enrolled until the DLT period for dose level 1 has been completed and it has been determined that the treatment schedule is safe. Patients must be positive for MRD disease as

Date of protocol: 10/14/2020

IRB Approval Date: 11/24/2020

Version of protocol: 7

IND number: 139015

Institutional protocol number: OSU 17102

[figure not shown]
determined by the combined analyses of flow cytometry, genomic sequencing and cytogenetics. Patients who do not demonstrate evidence of MRD in all three methods will not be eligible for the trial.

Bone marrow biopsies are done at the completion of 8 weeks. The maximal tolerated dose of DLI is chosen for expansion to the phase II portion of the study.

If patients are found to be in CR at the end of 8 weeks and treating physician concludes that patient continues to benefit from treatment, patients may proceed to Daratumumab maintenance with a schedule of 16mg/kg every 2 weeks for 16 weeks (8 doses) and then monthly for 6 months .

For patients with rapidly progressive disease despite 4 doses of Daratumumab, they will come off trial.

The dose level that is deemed safe will be chosen for the phase II portion of the study.

Dose level	Sibling donor	Unrelated donor	Haploidentical donor

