## 16 STATISTICAL CONSIDERATIONS

Study design/Sample size

This is a phase I/II study evaluating the combination of Daratumumab and escalating doses of DLI in patients with relapsed AML or transformed from MDS to AML post allo-HCT. Three dose levels will be used for related sibling donors and unrelated donors respectively.

Study Design: The standard 3+3 design will be applied to determine MTD of donor lymphocyte infusion when given with a fixed dose of Daratumumab. The dose escalation process for related sibling donor and unrelated donor will be conducted concurrently, but separately.

Dose escalation will proceed within each cohort according to the following scheme.

Number of Subjects with DLT at a Given Dose Level	Escalation Decision Rule
0 out of 3	Enter 3 subjects at the next dose level.
1 out of 3	
Enter 3 more subjects at this dose level.
 

• If 0 of these 3 subjects experience DLT, proceed to the next dose level.

• If 1 or more of this group suffer DLT, then dose escalation is stopped, and this dose is declared the maximally administered dose. Three (3)

Date of protocol: 10/14/2020

IRB Approval Date: 11/24/2020

Version of protocol: 7

IND number: 139015

Institutional protocol number: OSU 17102

	additional subjects will be entered at the next lowest dose level if only 3 subjects were treated previously at that dose.
>2	Dose escalation will be stopped. This dose level will be declared the maximally administered dose (highest dose administered). Three (3) additional subjects will be entered at the next lowest dose level if only 3 subjects were treated previously at that dose.
<1 out of 6 at highest dose level below the maximally administered dose	This is generally the recommended maximally tolerated dose.

The MTD will be defined as the highest safely tolerated dose where at most one patient in six experiences DLT during DLT observation period. The DLT observation period is defined as below.

Dose Level	DLT observation period
1	From the first dose of Daratumumab till 7 days post 3 rd dose
2/3	From the first dose of Daratumumab till at least 4 weeks post DLI

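### Phase I escalates DLI, but at levels 2-3 the DLT rules do not require the post-DLI window to be completed and do not count most non-hematologic toxicity attributed to DLI alone

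*Combined protocol and SAP*

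**What the plan says.** **Aim.** Section 16 states: "The standard 3+3 design will be applied to determine MTD of donor lymphocyte infusion when given with a fixed dose of Daratumumab". The MTD is the highest dose with a DLT in at most one of six patients during the observation period. At levels 2 and 3 that period is defined as "From the first dose of Daratumumab till at least 4 weeks post DLI".

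**Who counts.** For levels 2 and 3, section 16 makes a patient unevaluable and replaceable "if a patient does not receive 3 doses of Daratumumab and DLI due to reasons other than toxicity". The synopsis treats every patient as evaluable except those unable to receive "3 doses of daratumumab and DLT for dose levels 2 and 3 due to progression of AML" (the second DLT there is evidently meant to read DLI). Both rules concern treatment received. The accrual calculation in section 16 rests on another principle: "We assume that 10% of the patients in this group will not be evaluable due to not finishing the DLT observation period".

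**Who leaves early.** Section 7.1: "For patients with rapidly progressive disease despite 4 doses of Daratumumab, they will come off trial"; section 16.3 repeats this. In the synopsis, under special situations: "If patients attain response before DLI, there will be three options at the discretion of treating physician". Besides DLI, the options are daratumumab maintenance and "Proceed with second transplant".

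**What counts.** The synopsis and section 9.6 count severe acute GVHD whatever its attribution, severe non-hematologic toxicity if it is related to daratumumab, and unresolved Grade 4 hematologic toxicity not due to the disease. Immune-related events that respond to steroids and improve within 4 weeks are exempt. Section 10.3 records relatedness to DLI on its own scale, but no DLT rule uses it.

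**The concern.** In a 3+3 design, three to six patients decide each level, so the definitions of an evaluable patient and a countable event largely determine the result. Here the escalated component is DLI, and the window was set to see 4 weeks after it. A rule that asks only for exposure lets a patient with a short post-DLI observation stand in the denominator as free of DLT. A rule tied to daratumumab leaves out toxicity that the investigator attributes to the escalated component alone. Both act in one direction, towards clearing a DLI level that is too toxic. The MTD is the Phase I primary endpoint and sets the Phase II dose.

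**Working it through.** **1. The plan's accrual figure.** Per donor cohort, 3/0.9 = 3.33, so 4, and 18/0.9 = 20; two cohorts give 8-40. This matches sections 7.2 and 16. The inflation is for patients who do not finish the window, so the calculation assumes that they are replaced. The replacement rule in the same section does not say so.

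**2. Post-DLI days observed after removal for progression.** Inputs: doses on days 15, 22 and 29 (calendar, 12.1.3); DLI within 72 hours after a dose (9.3); removal after four doses (7.1, 16.3); patients seen before each dose (synopsis). Dose 4 falls on day 22, so the next scheduled visit is day 29.
- DLI with dose 4, days 22-25: 29 - 25 = 4 to 29 - 22 = 7 days, or 14%-25% of 28.
- DLI with dose 3, days 15-18: 29 - 18 = 11 to 29 - 15 = 14 days, or 39%-50% of 28.

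Such a patient has had three doses plus DLI, so neither rule replaces them. Section 12.4 regards removal for progression as completion of the study, and section 12.5 provides GVHD follow-up for patients in remission. Section 13.6 still requires adverse events to be recorded and unresolved SAEs to be followed, but no GVHD or DLT assessment is scheduled to 4 weeks post DLI.

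**3. Responder at level 2 or 3 who does not proceed to DLI.** Synopsis: DLI was not missed because of progression, so the patient is evaluable. Section 16: DLI was missed for a reason other than toxicity, so the patient is replaced. The two rules give opposite answers.

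**4. Effect on escalation (illustration only).** Assumptions: true DLT probability p = 1/3, onset uniform over the 28 post-DLI days, one of the first three patients seen for d days, all others seen in full. With q = 1 - p:

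P(escalate) = P(0 of 3) + P(1 of 3) × q³

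- Full observation: q³ + 3pq² × q³ = 0.2963 + 0.4444 × 0.2963 = 0.428.
- One patient seen for d days has counted probability p_d = p × d/28. Then P(0 of 3) = q²(1 - p_d) and P(1 of 3) = q²p_d + 2pq(1 - p_d). At p = 1/3, q² = 2pq = 4/9, so P(1 of 3) = 4/9 for every d, and P(escalate) = 0.4444(1 - p_d) + 0.1317.

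| d | p_d | P(escalate) |
|---|---|---|
| 28 | 0.333 | 0.43 |
| 14 | 0.167 | 0.50 |
| 11 | 0.131 | 0.52 |
| 7 | 0.083 | 0.54 |
| 4 | 0.048 | 0.55 |

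**5. Attribution.** The documents give no rate of toxicity attributed to DLI alone. If it made up an assumed share s of all DLTs, the counted rate would be p(1 - s). At p = 1/3, s = 5%, 10% and 25% give P(escalate) = 0.46, 0.49 and 0.60. The lower end is more plausible: the daratumumab scale includes a possible relation, and DLI follows a dose within 72 hours, so few events would be attributed to DLI only.

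**6. Calendar.** Section 7.1 allows DLI up to week 5, days 29-32, with the window ending on days 57-60. The last marked GVHD and adverse-event assessment is day 50, which is 18-21 days post DLI. The day 57-71 visit exists, with a marrow, but those two cells are blank.

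**The case against.** The best reply is that section 16 already contains the principle: the 10% sentence calls non-finishers unevaluable, the MTD is defined on events in the observation period, and section 16.3 places the review after the third patient's window. Completion was probably intended. That stands as a reading of intent, but it sits in an accrual assumption, and the two rules that tell the team whom to replace say something else.

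The second gap is limited. Acute GVHD, the main DLI risk named in the plan, counts without any attribution test, qualifying hematologic toxicity needs no link to daratumumab, and an event related to both agents counts.

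A reader might infer more than the documents support:
- *That a week-3 DLI also leaves only 4-7 days.* Removal follows four doses, and a patient removed on day 22 before treatment has had three.
- *That the plan's 10% are counted as DLT-free.* Section 16 calls them unevaluable.
- *That a patient who never received DLI will count.* This needs the synopsis to override section 16, which replaces that patient.
- *That the synopsis sentence opening the next level 2 weeks after DLI, on absence of GVHD alone, exposes the next patients too soon.* The next level's DLI comes no earlier than day 15, so at least 14 + 14 = 28 days after the previous one. The sentence conflicts with the decision rule in sections 16 and 16.3, and no more.

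Weekly safety calls (14.1), the enrollment hold after Grade 3-4 GVHD (9.6) and adverse-event recording (13.6) reduce the risk. They do not settle who or what counts.

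**Conclusion.** The point holds. At levels 2-3 the evaluability and replacement rules are based on exposure, do not match the 4-week post-DLI window, and conflict with the section's own accrual allowance; the synopsis and section 16 also conflict with each other on responders who skip DLI. Followed literally, they keep a patient with about 4-7 (week-4 DLI) or 11-14 (week-3 DLI) of 28 post-DLI days in the denominator as DLT-free. These day counts come from the plan's own schedule, taking removal at the next weekly visit.

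The escalation probabilities, 0.43 rising to 0.50-0.55, concern the step from level 2 to 3. They depend on an assumed DLT rate and onset pattern, and on one such patient being among the first three; they show direction and rough size and are not a forecast. The attribution gap is real but narrow, and the documents cannot size it.

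**What to change.** 1. In the synopsis and section 16, define DLT-evaluable at levels 2-3 as: had a DLT in the window, or received three daratumumab doses plus DLI and was followed through 4 weeks post DLI. Replace all others, including responders who do not receive DLI. The team should note that a patient who misses DLI for a toxicity short of a DLT, whom section 16 does not replace at present, would then be replaced.
2. Continue GVHD and DLT assessment to 4 weeks post DLI after removal for progression, and mark GVHD and adverse-event assessment at the existing day 57-71 visit.
3. In the synopsis and section 9.6, let the non-hematologic clause cover toxicity related to daratumumab, DLI or the combination, using the attribution already collected under section 10.3. Keep the exemption for steroid-responsive immune events.
4. Align the two-week enrollment sentence in the synopsis with the DLT window in sections 16 and 16.3.

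The cost is protocol wording, some assessments after removal, a few more replaced patients (partly covered by the plan's 10%), and a short delay at the level 2-to-3 step, up to about 2 weeks compared with the two-week sentence.

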## 9.2 DARATUMUMAB INFUSION RELATED REACTIONS

For infusion reactions of any grade/severity, immediately interrupt the DARATUMUMAB infusion and manage symptoms. Management of infusion reactions may further require reduction in the rate of infusion, or treatment discontinuation of DARATUMUMAB as outlined below.

- Grade 1-2 (mild to moderate): Once reaction symptoms resolve, resume the infusion at no more than half the rate at which the reaction occurred. If the patient does not experience any further reaction symptoms, infusion rate escalation may resume at increments and intervals as clinically appropriate up to the maximum rate of 200 mL/hour.
- Grade 3 (severe): Once reaction symptoms resolve, consider restarting the infusion at no more than half the rate at which the reaction occurred. If the patient does not experience additional symptoms, resume infusion rate escalation at increments and intervals as clinically appropriate. Repeat the procedure above in the event of recurrence of Grade 3 symptoms. Permanently discontinue DARATUMUMAB upon the third occurrence of a Grade 3 or greater infusion reaction.
- Grade 4 (life threatening): Permanently discontinue Daratumumab treatment.

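### The DLT replacement rule has no exception for a patient who has already had a DLT, so an observed DLT can leave the 3+3 count

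*Combined protocol and SAP*

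**What the plan says.** Section 16 sets the replacement rule by dose level. At level 1, a patient who "receives less than 3 doses of Daratumumab due to reasons other than toxicity, then this patient will not be evaluable for DLT" and is replaced. At levels 2 and 3, the same follows if the patient "does not receive 3 doses of Daratumumab and DLI due to reasons other than toxicity, then this patient will not be evaluable".

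The DLT observation period in the same section starts earlier than the treatment that the rule requires. For levels 2 and 3 it runs "From the first dose of Daratumumab till at least 4 weeks post DLI"; for level 1 it runs from the first dose to 7 days after the third. The MTD is the highest dose at which no more than one patient in six has a DLT in that period.

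The synopsis row on DLT evaluability is worded differently: "All patients are evaluable for DLT except patients who are unable to receive 3 doses of daratumumab in dose level 1", or the corresponding treatment "for dose levels 2 and 3 due to progression of AML". That row prints DLT where DLI appears to be meant, and it is unclear whether the progression condition also governs level 1.

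Neither place says what happens to a patient who had a DLT and then missed treatment for another reason.

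**The concern.** The phase I primary endpoint (Section 16.1) is the MTD, and a 3+3 design settles it on counts of zero, one or two DLTs. Section 16 counts a DLT from the first daratumumab dose, but its replacement rule looks only at the reason for the missed treatment. A patient with a DLT at dose 1 who later misses DLI because the leukemia progressed is counted under one sentence and removed under the other.

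The protocol's own pathways allow this sequence. Section 9.6 makes a DLT of "Any Grade 3-4 non-hematologic toxicity related to Daratumumab". A Grade 3 infusion reaction would meet that, unless it is classed under the carve-out for steroid-responsive immune-related events. Section 9.2 then allows treatment to go on: "Once reaction symptoms resolve, consider restarting the infusion at no more than half the rate at which the reaction occurred". The DLT therefore need not be the reason why later treatment is missed. Section 7.1 supplies one non-toxicity exit: "For patients with rapidly progressive disease despite 4 doses of Daratumumab, they will come off trial". At levels 2 and 3 that exit can come before DLI, which may be given up to week 5.

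At stake is whether a level is expanded, passed or stopped, and so which DLI dose goes into the 25-patient phase II.

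**Working it through.** **1. The plan's own figure.** Section 16 takes 3 to 18 DLT-evaluable patients per cohort, assumes 10% not evaluable, and arrives at 4 to 20. This reproduces: 3/0.9 = 3.33, rounded up to 4; 18/0.9 = 20.

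**2. Effect of one removed DLT.** Suppose the replacement has no DLT. A level at 1/3 (add three patients) is recorded as 0/3 (escalate). A level at 2/6 (stop) is recorded as 1/6 (meets the MTD criterion). If the replacement also has a DLT, the count is unchanged.

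**3. Probability of clearing a level.** The documents give no DLT rate and no loss rate by DLT status, so these are assumptions:
- p: true DLT rate;
- u1: chance that a patient with a DLT later misses required treatment for a non-toxicity reason;
- u0: the same chance for a patient without a DLT.

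Formulas:
- Clearing a level at counted rate q: C(q) = (1−q)³ + 3q(1−q)²(1−q)³.
- Counted rate under the rule as written: p(1−u1) / [p(1−u1) + (1−p)(1−u0)].
- Counted rate if every DLT is kept: p / [p + (1−p)(1−u0)].
- Nominal probability (no losses): C(p).

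| p | u1 | u0 | Counted rate, as written | Clears, as written | Nominal | Counted rate, DLTs kept | Clears, DLTs kept |
|---|---|---|---|---|---|---|---|
| 20% | 10% | 10% | 20.0% | 70.9% | 70.9% | 21.7% | 67.1% |
| 20% | 5% | 10% | 20.9% | 69.0% | 70.9% | 21.7% | 67.1% |
| 30% | 10% | 10% | 30.0% | 49.4% | 49.4% | 32.3% | 44.9% |
| 30% | 30% | 10% | 25.0% | 60.0% | 49.4% | 32.3% | 44.9% |
| 40% | 30% | 10% | 34.1% | 41.2% | 30.9% | 42.6% | 26.9% |

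For example, in row 4 the counted rate as written is 0.21/(0.21 + 0.63) = 0.25, and C(0.25) = 0.422 + 0.178 = 0.600. The total share lost in that row is 0.3 × 0.3 + 0.7 × 0.1 = 16%, above the plan's 10%.

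**4. How often a DLT would be removed.** Among the first three treated patients, the chance of at least one removed DLT is 1 − (1 − p·u1)³. This is 5.9% at p = 20%, u1 = 10%; 8.7% at p = 30%, u1 = 10%; and 24.6% at p = 30%, u1 = 30%.

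**5. Which DLTs are exposed.** At levels 2 and 3 the rule cannot remove a patient who has had three doses and DLI, so every DLT after that point counts, including GVHD caused by the DLI. Because u1 averages over all DLT patients, it falls as more of the DLTs occur after DLI.

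**The case against.** A reader might infer that the rule errs only towards clearing a level. The documents do not support that. The rule also removes patients without a DLT, which pushes the other way. When u1 = u0 the two effects cancel and the level clears at the nominal probability whatever the loss rate; when u1 is below u0 (row 2), it clears slightly less often than nominal.

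A reader might also take the historical median survivals of 51 and 84 days in Section 4.1, assume exponential survival, and infer that 25% to 38% of patients are lost by Day 35 (1 − 0.5^(35/84) and 1 − 0.5^(35/51)). At a 20% DLT rate that gives 71% clearing as written against 60% to 52% with DLTs kept. It would be wrong to call this gap wrongful clearing: 71% is the nominal value, and the gap measures how cautious the alternative is. The loss rate is not the plan's either. Section 16 assumes 10%, Section 4.1 also gives a median of 3 to 6 months, enrolled patients are selected on performance status and organ function, and level 1 needs treatment only to Day 15.

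Other limits stand. A patient who stops because of toxicity stays evaluable. The synopsis enrollment schedule separately makes moving on from level 1 depend on there being no infusional toxicity or GVHD. A patient who responds and goes without DLI is non-evaluable only under Section 16, because the synopsis recognises AML progression alone. Section 9.6 holds enrollment after Grade 3-4 GVHD, and Sections 14.1 and 16.3 provide for safety calls and review. These reduce the risk, but none of them says that the observed DLT stays in the count.

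**Conclusion.** The gap is real: as written, a DLT observed before DLI, or before the third dose at level 1, can be dropped when the patient later misses treatment for a non-toxicity reason, and no other section restores it. It is a missing exception, not an instruction to discard DLTs. The two statements of the rule also conflict on which reasons qualify.

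Its size depends on whether DLT patients are lost more often than others, which the documents do not say. If losses are independent of DLT, the counted rate is unbiased; at a 20% DLT rate and 10% loss, keeping every DLT lowers clearing from 71% to 67%, which is caution and not correction of an error. If DLT patients are lost more often, the rule clears too often: 60.0% against 49.4% nominal, and 44.9% with DLTs kept, at an assumed 30% DLT rate with 30% of DLT patients and 10% of others lost. The plan gives no ground for assuming independence, and whether an observed DLT counts in a primary endpoint should not depend on which sentence is applied.

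**What to change.** Reconcile the synopsis row on DLT evaluability with Section 16, including which reasons for missed treatment qualify and the apparent DLT/DLI misprint, and put the same sentence in both:

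*A patient who has a DLT during the DLT observation period is evaluable and counted as a DLT regardless of doses or DLI received; only patients without a DLT may be declared non-evaluable and replaced.*

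The cost is one sentence in two places. It changes no dose, no treatment rule and not the planned range of 4 to 20 patients per cohort. The downside is that a level may be expanded or stopped slightly more often, because every DLT is kept while some patients without a DLT are still replaced.
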